Unique Protocol ID: 2024-01/33

Official Title: Effect of Postoperative Oral Rinsing on Thirst-Related Discomfort, Comfort Level, and Bowel Movement in Individuals Undergoing Abdominal Surgery: A Randomized Controlled Trial

NCT ID not yet assigned

Date of Document: January 18, 2024

Study Design

This study was conducted as a randomized controlled trial with pre-test and post-test design, involving intervention and control groups.

Study Setting and Duration

The research was carried out at the Department of General Surgery, Sivas Cumhuriyet University Research and Training Hospital, between June 5 2024, and December 5, 2024.

Study Population and Sample

The study population included patients who underwent abdominal surgery in the general surgery clinic during the study period. The sample size was calculated using G*Power 3.1.9.7 software by a biostatistics expert. With an effect size of 0.50, $\alpha=0.05$, and power=0.85 ($\beta=0.15$), the required sample size was determined to be 82 patients (41 in the intervention group and 41 in the control group). The actual study was completed with 98 patients (49 per group), considering potential data loss. Eligible patients were stratified based on diagnosis and randomized using block randomization with a random number table in a 1:1 allocation ratio.

Inclusion and Exclusion Criteria

The study included patients who were able to communicate, aged 18 or older, agreed to participate, and were scheduled for elective surgery.

Patients were excluded if they were over 80 years old, had a mental disorder that prevented them from rinsing their mouth, were unconscious after surgery, were at risk of swallowing water during rinsing, and underwent emergency surgery.

Patients who refused to complete the post-test and those requiring intensive care after surgery were excluded.

Data Collection Tools

Four tools were used:

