1. Mini Mental State Assessment Test: The Mini Mental State Assessment (MMSA) is a common screening tool to systematically and comprehensively assess individuals' cognitive status. The test consists of 11 items assessing five cognitive domains: orientation, registration, attention and calculation, recall, and language. The maximum score that can be obtained from the scale is 30, and scores of 23 or below suggest cognitive impairment. The administration time, approximately 5–10 minutes, makes the tool suitable for routine use in clinical and research settings. Its validity and reliability in Turkish were conducted.

2. Personal Information Form: The questionnaire, which included the participants' descriptive and clinical characteristics, was developed by the researchers in two sections based on literature and clinical observations. The first section consisted of seven questions covering the patient's descriptive characteristics, including age, gender, and education level, in line with the study group, and the patient's clinical characteristics, including diagnosis, preoperative fasting time, postoperative oral intake time, and the time to start oral intake. The second section included a chart created for recording bowel sounds.

3. Surgical Period Thirst Discomfort Scale (SPTDS): The original seven-item scale was removed due to the low factor analysis of one item in the Turkish validity and reliability study. It was adapted as six items using a three-item Likert-type scale. Ratings are as follows: "Didn't Bother (0)," "A Little Bit Bothered (1), and "A Lot Bothered (2). The scale items are: "My Mouth is Dry," "My Lips are Dry," "My Saliva is Thick," "My Throat is Dry," "I Have a Bad Taste in My Mouth," and "I Want to Drink Water." The minimum score for the total scale is 0, and the maximum score is 12. As the score obtained from the scale increases, the level of discomfort related to thirst also increases.

4. Comfort Level Determination Scale - VAS: The comfort level of the individuals participating in the study will be determined using the Visual Analog Scale-10 (VAS-10). The scale is a 10-cm straight line with points spaced 1 cm apart. Each point on this straight line will be evaluated as a score for the comfort level, with the starting point being "0 = Lowest Comfort Level" and "10 = Highest Comfort Level." As the score obtained from the scale increases, the comfort level also increases.

Intervention Procedure

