To ensure consistency and avoid inter- or intra-group differences, all bowel sound assessments were performed using the same brand and model of stethoscope, and each patient's bowel sounds were auscultated for one minute. Considering the oral rinsing process, the total time required for data collection in the experimental group was approximately 20–25 minutes.

Data Analysis

SPSS 22.00 package program was used to analyze the data. Skewness-Kurtosis analyses were performed to determine the conformity of the data to a normal distribution. A Skewness-Kurtosis value between +1.96 and -1.96 is considered a normal distribution. All data used in the study were within the normal range, and the data showed a normal distribution. Frequency (n) and percentage (%) distributions were calculated to determine the sociodemographic and clinical characteristics of the participants. A t-test for independent samples was used to determine the mean differences between two independent groups, a t-test for dependent samples was used to compare pre- and post-intervention measurements, and a single-factor analysis of variance (ANOVA) was used for repeated measures. Cohen's d effect size was calculated to assess the significance of the difference between the groups in terms of the intervention. Statistical significance was accepted as $p<0.05$.

RESULTS

The mean age of the participants in the experimental group was 56.41 ± 14.80 years, while in the control group it was 55.78 ± 14.00 years. Overall, 57.1% of the participants were female. Among the patients, 46.9% of those in the experimental group and 42.9% in the control group were primary school graduates.

Clinically, 49% of the patients underwent surgery for cholecystectomy. The preoperative fasting period ranged between 7–18 hours in the experimental group, with a mean of 11.78 ± 2.47 hours, and between 8–36 hours in the control group, with a mean of 12.78 ± 4.33 hours.

The postoperative oral intake initiation time in the experimental group ranged between 6–20 hours, with a mean of 10.41 ± 4.64 hours, while in the control group it ranged between 2–66 hours, with a mean of 15.20 ± 11.57 hours. The

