difference between the two groups was statistically significant ($t=-2.635$, $p=0.010$), indicating that patients in the experimental group began oral intake earlier than those in the control group. All patients in the experimental group started oral intake within 6–24 hours, whereas 88% of the control group started within 6–24 hours, 8% between 24–48 hours, and 4% after more than 48 hours. This difference was also statistically significant ($\chi^2=6.391$, $p=0.041$), again showing that oral intake began earlier in the experimental group.

Before mouth rinsing, the mean VAS Comfort Level score in the experimental group was 3.59 ± 1.29 , the mean Surgical Thirst Discomfort Scale (SPTDS) score was 8.00 ± 2.84 , and the mean number of bowel sounds was 3.49 ± 1.06 . In the control group, the initial mean VAS Comfort Level score was 4.02 ± 1.71 , the mean SPTDS score was 8.14 ± 2.74 , and the mean number of bowel sounds was 4.06 ± 1.52 . No significant differences were found between the groups in terms of VAS Comfort Level ($t=1.399$, $p=0.165$) or SPTDS ($t=-0.253$, $p=0.801$), indicating similar baseline comfort and thirst discomfort levels. However, the difference in bowel sound frequency was significant ($p<0.05$), favoring the control group, with a moderate effect size (Cohen's $d=0.44$).

After oral rinsing, the mean VAS Comfort Level score in the experimental group increased to 7.33 ± 1.14 , while in the control group's second measurement it was 3.86 ± 0.94 . This difference was statistically significant ($t=16.438$, $p<0.001$), demonstrating that oral rinsing significantly improved comfort, with a very large effect size (Cohen's $d=3.32$).

The mean SPTDS score decreased to 1.31 ± 1.54 in the experimental group after oral rinsing, compared to 8.59 ± 2.15 in the control group's second measurement. The difference was statistically significant ($t=-19.269$, $p<0.001$), indicating that oral rinsing significantly reduced thirst-related discomfort, with a very large effect size (Cohen's $d=3.89$).

The mean number of bowel sounds increased to 5.98 ± 1.61 in the experimental group after oral rinsing, whereas it was 3.86 ± 1.22 in the control group's second measurement. This difference was statistically significant ($t=7.334$, $p<0.001$), suggesting that oral rinsing enhanced bowel motility, with a large effect size (Cohen's $d=1.48$).

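### Time to oral intake is not a named outcome, yet Results test it twice on the same patients and read the second test as confirmation; more than half of the mean gap comes from six late control patients.

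*Combined protocol and SAP*

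**What the plan says.** The title gives the trial's scope: "Effect of Postoperative Oral Rinsing on Thirst-Related Discomfort, Comfort Level, and Bowel Movement in Individuals Undergoing Abdominal Surgery". Oral intake is not in it. Under Data Collection Tools, the Personal Information Form records "the patient's clinical characteristics, including diagnosis, preoperative fasting time, postoperative oral intake time, and the time to start oral intake". Two oral-intake items are listed and neither is defined. Data Analysis does not name either as an endpoint.

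Intervention Procedure describes two administrations of the forms: before the first rinse and 15 minutes after the last, with controls reassessed 75 minutes after their first assessment. No later follow-up is described.

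In RESULTS, oral-intake time in the rinse arm "ranged between 6–20 hours, with a mean of 10.41 ± 4.64 hours"; the control sentence continues "while in the control group it ranged between 2–66 hours, with a mean of 15.20 ± 11.57 hours". A t-test is printed (t=-2.635, p=0.010) and read as an earlier start in the rinse arm. The times are then grouped. All rinse patients fall in 6–24 h; controls split 88%, 8% and 4% over 6–24 h, 24–48 h and beyond 48 h. The paragraph ends: "This difference was also statistically significant ($\chi^2=6.391$, $p=0.041$), again showing that oral intake began earlier in the experimental group".

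**The concern.** Three things weaken the result. First, nothing in the document plans oral-intake time as an outcome, so its significance test is unplanned, and no multiplicity handling is described. Second, the t-test and the chi-square use the same patients and the same variable. The second test cannot corroborate the first, yet the text offers it as repeat evidence. Third, the control distribution has a long right tail: its minimum is (15.20 − 2)/11.57 = 1.1 SD below the mean and its maximum is (66 − 15.20)/11.57 = 4.4 SD above. A comparison of means is then sensitive to a few patients.

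This is also the only reported comparison of something that may have happened after the 75-minute window. A reader could take it as support for the bowel-recovery claim, so its status and robustness should be plain.

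**Working it through.** **Inputs (RESULTS; Study Population and Sample for n).** 49 per arm. Rinse: mean 10.41, SD 4.64, range 6–20 h. Control: mean 15.20, SD 11.57, range 2–66 h; categories 88/8/4%.

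**1. Reproduce the chi-square.** 88%, 8% and 4% of 49 are 43.12, 3.92 and 1.96, that is 43/4/2. Against 49/0/0, the expected counts in each arm are 46, 2 and 1.

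χ² = 2 × [(3²/46) + (2²/2) + (1²/1)] = 2 × (0.1957 + 2 + 1) = 6.391; df 2, p = 0.041.

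This matches the printed result and fixes the number of controls after 24 h at six. Four of the six expected counts are below 5. Fisher's exact test on 0/49 against 6/49 gives p = 0.027; the exact 2×3 test gives the same.

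**2. Try to reproduce the t-test.** SE = √[(4.64² + 11.57²)/49] = √(155.39/49) = 1.781, so t = −4.79/1.781 = −2.690 (p = 0.008), not −2.635. Rounding does not explain this: with the smallest gap (4.78) and largest SDs (4.645, 11.575) that the rounding allows, t is −4.78/1.782 = −2.68.

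**3. How much of the 4.79 h gap rests on the six?** Control total: 49 × 15.20 = 744.8 h. Control sum of squares about the mean: 48 × 11.57² = 6425.5. The six comprise four patients in 24–48 h, one in 48–66 h and one at 66 h.

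- *Late times as early as allowed:* 4 × 24 + 48 + 66 = 210 h. The other 43 average (744.8 − 210)/43 = 12.44 h. Residual gap 12.44 − 10.41 = 2.03 h; share due to the six (4.79 − 2.03)/4.79 = 58%.
- *Late times as late as the printed SD permits:* keep one at 48 and one at 66, and raise the four together. At 37.5 h each, the total is 264 h and the other 43 average 480.8/43 = 11.18 h. The squares are 2580.6 + 1075.8 + 4 × 22.3² (1989.2) + 43 × (11.18 − 15.20)² (about 694), plus about 86 for having one of the 43 at 2 h and the rest equal. The sum is about 6426, so the allowance is used up. Residual gap 0.77 h; share 84%.

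**4. t-test without the six.** In the 58% case the SD of the other 43 is √[(6425.5 − 3966.2 − 328.3)/42] = 7.12. Pooled SD = √[(48 × 4.64² + 42 × 7.12²)/90] = 5.93; t = 2.03/[5.93 × √(1/49 + 1/43)] = 1.64, p = 0.11. A search over feasible configurations gave p of about 0.06 to 0.29.

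**5. Internal consistency.** The control minimum is 2 h, but the lowest printed category starts at 6 h and 88 + 8 + 4 = 100%. The 2 h patient fits no category.

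**The case against.** The strongest reply is that the text claims little. It says the rinse arm began oral intake earlier. Where the authors claim an effect, on comfort, thirst and bowel motility, they name rinsing as the cause; here they do not, and the CONCLUSION omits oral intake. A reader might infer that the report presents earlier feeding as a benefit of rinsing, but the documents do not say so. This stands.

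Second, removing the latest patients from one arm selects on the outcome. If the six latest rinse patients were also removed, taking the extreme case of 20 h each, the other 43 would average (49 × 10.41 − 120)/43 = 9.07 h. Against 11.18–12.44 h, a gap of 2.1–3.4 h (44–70% of 4.79) would remain. A real difference in a time variable may also lie in its tail, and the late-start imbalance has exact p = 0.027. This stands too: the check shows dependence on a few patients, not that the difference is false.

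Third, a reader might blame case mix, since 49% of operations were cholecystectomies. Randomisation was stratified by diagnosis, which is meant to limit such imbalance, and no diagnosis split by arm is given. That explanation is conjecture.

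Fourth, the 75-minute schedule does not prove that the times were not observed; a later chart entry is possible. What survives is that the method of ascertainment is not stated.

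None of this rescues the use of the second test as confirmation, or supplies a plan for the comparison.

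**Conclusion.** The point holds as one of reporting and status. An unplanned comparison is reported as significant twice from one set of values, with the second test offered as support for the first. Six of 49 controls account for about 58–84% of the mean gap when left out as a sensitivity check, with 0.8–2.0 h of 4.79 h remaining. The range assumes that the printed mean, SD, range and category counts are correct; individual times are not given. The 2 h minimum and the t statistic show that the printed figures do not fully agree, so the bounds are approximate.

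The difference is fragile and exploratory. It is not shown to be spurious, and no named outcome or stated conclusion depends on it.

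**What to change.** - Delete the clause that presents the chi-square as repeat evidence, and label the comparison exploratory and unplanned.
- Define the two oral-intake items. State how and when the time was recorded, and whether it is a planned time or an observed event.
- Replace the two tests with one exact or rank-based comparison stratified by diagnosis (for example a van Elteren test). Give medians and quartiles by arm and within the diagnosis strata used for randomisation.
- List the diagnoses of the six late starters.
- Do not move the variable to a baseline table unless it is confirmed to be a planned time set before the intervention; otherwise a post-randomisation event would be shown as baseline.
- Reconcile the 2 h control minimum with the categories, and the printed t of −2.635 with the −2.690 implied by the printed means and SDs.

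The cost is rewording and one table from data that the form already collects. Some strata may be too small for informative quartiles. One favourable-looking result becomes exploratory.

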Before initiating the main study, a pilot application was conducted with a total of eight patients—four from the experimental group and four from the control group—to evaluate the data collection instruments and the implementation process. The results of the pilot study indicated that all scale items were found to be clear and understandable by the participants, and the average response time ranged between 10 and 12 minutes. No technical or logistical problems were encountered during the process, and the main study was subsequently initiated. Data obtained from the pilot study were not included in the main sample.

During the pilot phase, data collection instruments were administered to the experimental group patients after each oral rinse. However, as patients provided near-perfect responses across all measurements, a potential risk of bias was identified. Therefore, in the main study, the data collection instruments were administered only before the first oral rinse and after the completion of all three rinses.

The purpose of the study was explained to all participants, and written informed consent was obtained. Data were collected face-to-face by the researchers.

In the experimental group, postoperative cognitive assessment was conducted, and patients scoring 23 or higher on the MMSE (Mini-Mental State Examination) were instructed to perform oral rinsing three times at 20-minute intervals, each time using 20 ml of distilled water. Two graduated plastic cups were used for each rinsing: one containing 20 ml of distilled water and one empty cup for spitting out the rinse water. This setup enabled the evaluation of whether patients swallowed the water; none of the patients did, and all participated in the procedure compliantly. Data collection forms were administered face-to-face before the first rinse and 15 minutes after the final rinse, and bowel sounds were auscultated.

In the control group, postoperative cognitive assessment was also conducted, and patients scoring 23 or higher on the MMSE were administered the data collection forms and had their bowel sounds auscultated. No intervention was applied to this group. The data collection forms were re-administered 75 minutes later, in a manner consistent with the experimental group, and bowel sounds were re-evaluated.

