Within-group comparisons showed that in the experimental group, post-rinsing measurements demonstrated an increase in comfort level, a decrease in thirst-related discomfort, and an increase in bowel motility compared to pre-rinsing values. In contrast, no significant changes were observed between the two measurements in the control group.

These findings indicate that oral rinsing led to significant improvements in comfort, reduction of thirst-related discomfort, and stimulation of bowel motility in the experimental group, while no meaningful changes occurred in the control group.

CONCLUSION

In conclusion, oral rinsing with plain water is an effective, cost-free, and easily applicable method for reducing postoperative thirst discomfort, enhancing comfort, and accelerating bowel movements. It is recommended that this practice be integrated into routine care in surgical clinics.

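### RESULTS infers a rinse effect from separate within-arm comparisons and restates non-significance in controls as absence of meaningful change (minor; significance of the between-arm results is unaffected)

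*Combined protocol and SAP*

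**What the plan says.** Data Analysis names three mean-comparison methods: an independent-samples t-test between groups; a paired test ("a t-test for dependent samples was used to compare pre- and post-intervention measurements"); and an ANOVA ("a single-factor analysis of variance (ANOVA) was used for repeated measures"). Intervention Procedure explains that, after the pilot, the instruments were "administered only before the first oral rinse and after the completion of all three rinses", so each patient has two readings. Controls were re-measured after 75 minutes.

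RESULTS first gives the between-arm comparisons at baseline and post-test. For VAS comfort and SPTDS it reads the non-significant baseline tests as "indicating similar baseline comfort and thirst discomfort levels". It discloses a significant baseline difference in bowel sounds (d = 0.44).

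The within-group paragraph follows. It reports improvement on all three outcomes in the rinse arm and then says: "In contrast, no significant changes were observed between the two measurements in the control group". The closing paragraph attributes the improvements to rinsing and adds "while no meaningful changes occurred in the control group". No paired t, p-value, SD of change, confidence interval or margin for a meaningful change is printed for either arm.

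**The concern.** Two steps in the closing paragraphs do not follow.

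1. **A change in one arm and a non-significant change in the other is not a comparison of the arms.** Each paired test mixes any rinse effect with time since surgery, retesting and regression to the mean. The randomised control group removes these only when the arms are compared directly.
2. **Not significant becomes not meaningful.** The second statement needs an interval for the change and a stated margin. The documents give neither. The baseline wording on VAS and SPTDS makes the same step.

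The planned ANOVA does not help. With one factor (time) and two readings, it repeats the paired test and has no term for arm.

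At stake is a printed statement about controls that the analysis cannot support. In addition, change from baseline is examined only inside each arm and never compared between arms. That matters for bowel sounds, where the arms started apart.

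**Working it through.** **Inputs** (RESULTS; n = 49 per arm from Study Population and Sample). The pre-post correlation r is not given, so it is assumed and varied. Two-sided 5% is assumed.

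| Outcome | Rinse pre | Rinse post | Control pre | Control post |
|---|---|---|---|---|
| VAS comfort | 3.59 (1.29) | 7.33 (1.14) | 4.02 (1.71) | 3.86 (0.94) |
| SPTDS | 8.00 (2.84) | 1.31 (1.54) | 8.14 (2.74) | 8.59 (2.15) |
| Bowel sounds | 3.49 (1.06) | 5.98 (1.61) | 4.06 (1.52) | 3.86 (1.22) |

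**Step 1. Reproduce the printed post-test comparisons.** SE = √((s₁² + s₂²)/49); 95% CI = difference ± 1.985 × SE (96 df).

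- VAS: 3.47 / √((1.2996 + 0.8836)/49) = 3.47/0.2111, t = 16.44 (printed 16.438); CI 3.05 to 3.89.
- SPTDS: -7.28/0.3778, t = -19.27 (printed -19.269); CI -8.03 to -6.53.
- Bowel sounds: 2.12/0.2886, t = 7.35 (printed 7.334, inside the range 7.287 to 7.407 that rounding of the inputs allows); CI 1.55 to 2.69.

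All three reproduce.

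**Step 2. Change in controls.** SD_diff = √(s₁² + s₂² - 2·r·s₁·s₂); CI = change ± 2.011 × SD_diff/7 (48 df). For SPTDS at r = 0.5, SD_diff = √(7.5076 + 4.6225 - 5.891) = 2.498.

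| Control change | r = 0 | r = 0.5 | r = 0.8 |
|---|---|---|---|
| VAS -0.16 | -0.72 to 0.40 | -0.59 to 0.27 (p = 0.45) | -0.48 to 0.16 |
| SPTDS +0.45 | -0.55 to 1.45 | -0.27 to 1.17 (p = 0.21) | -0.02 to 0.92 |
| Bowel sounds -0.20 | -0.76 to 0.36 | -0.60 to 0.20 (p = 0.32) | -0.46 to 0.06 |

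Solving |change| × 7/SD_diff = 2.011 for r gives the correlation above which each change would be significant: 0.82 for SPTDS, 0.89 for bowel sounds and 1.09 (impossible) for VAS. Even at r = 1, the VAS t is 0.16 × 7/0.77 = 1.45. The reported lack of significance in the means is therefore compatible with the printed figures.

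**Step 3. The ANOVA.** With two repeated readings, F(1,48) = t² from the paired test. It gives the same p-value and no arm contrast.

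**Step 4. Between-arm test of change.** Difference in mean change, rinse minus control, with 95% CI:

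| Outcome | Difference | r = 0 | r = 0.9 |
|---|---|---|---|
| VAS | 3.90 | 3.16 to 4.64 | 3.59 to 4.21 |
| SPTDS | -7.14 | -8.49 to -5.79 | -7.71 to -6.57 |
| Bowel sounds | 2.69 | 1.91 to 3.47 | 2.39 to 2.99 |

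The smallest |t| is 6.87 (bowel sounds, r = 0).

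For the baseline-adjusted (ANCOVA) estimate, the pooled slope for bowel sounds is r × (1.06·1.61 + 1.52·1.22)/(1.06² + 1.52²) = 1.037r. The estimate is 2.12 + 1.037r × 0.57, which is 2.12 at r = 0, 2.42 at r = 0.5 and 2.65 at r = 0.9. The change-score estimate is 2.12 + 0.57 = 2.69. Over the same range, ANCOVA gives 3.47 to 3.73 for VAS and -7.28 to -7.20 for SPTDS.

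**Step 5. Baseline differences** (rinse minus control, SE as in step 1):

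- VAS -0.43 (SE 0.306), CI -1.04 to 0.18.
- SPTDS -0.14 (SE 0.564), CI -1.26 to 0.98.
- Bowel sounds -0.57 (SE 0.265), CI -1.10 to -0.04; t = -2.15, p = 0.034.

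**Step 6. Spread of control VAS.** The variance ratio is 2.924/0.884 = 3.31. The Pitman-Morgan statistic is (s₁² - s₂²)·√47/(2·s₁·s₂·√(1 - r²)). At r = 0 this is 2.0405 × 6.856/3.2148 = 4.35 (p = 0.00007), and it rises with |r|. Approximate normality is assumed.

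**The case against.** The strongest reply is that the effect claims are made earlier in RESULTS, from independent-samples tests on all three outcomes, each with p < 0.001, and that the within-group paragraph only adds description. The closing paragraph could also be read as summing up the whole section. Much of this stands. The between-arm tests reproduce, and comparing changes between arms alters no conclusion on significance. What does not stand is the statement about controls: no between-arm test can show that controls did not change.

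It can also be said that the control intervals are narrow beside the between-arm differences. That is true, but no margin is stated against which to call them negligible.

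Three stronger readings are tempting, and the documents do not support them.

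- **A reader might infer that the efficacy claims depend on the within-arm contrast.** They do not, because the direct comparisons are printed.
- **A reader might infer that the control SDs contradict the reported lack of significant change.** That sentence concerns paired readings compared by t-test. For VAS, non-significance is certain at any r; for the other two outcomes a contradiction would need r above about 0.82 or 0.89, and no r is given. The fall in VAS SD shows a change in spread, which justifies a data check and no more.
- **A reader might attach an error rate to the argument.** If both arms changed equally and each paired test had power π, the pattern would arise with probability π(1 - π), at most 25%. The between-arm results rule out equal change, so that figure does not apply here.

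The ANOVA is redundant rather than harmful: no result from it is printed and no claim uses it.

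**Conclusion.** The point holds as a minor reporting and inference fault. The within-arm contrast is not a between-arm test, and the claim of no meaningful change in controls is unsupported without an interval and a margin. The same applies to the wording on baseline similarity.

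Significance of the three between-arm results would not change (|t| at least 6.87 for change scores at r from 0 to 0.9). The numerical consequence is mainly for bowel sounds. The unadjusted estimate of 2.12 becomes 2.12 to 2.65 with baseline adjustment, depending on r, and 2.69 on change scores, up to 0.57/2.12 = 27% larger.

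These figures rest on the printed means and SDs, 49 per arm, two-sided 5% and an assumed r common to both arms. Individual data would replace the assumption about r.

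**What to change.** - **Data Analysis:** state that the paired t-tests are descriptive. Remove the single-factor repeated-measures ANOVA.
- **RESULTS, within-group and closing paragraphs:** delete the inference from within-group significance and the claim of no meaningful change in controls. Give each arm's mean change with its SD and 95% CI.
- **RESULTS, effect claims:** base each on the between-arm difference with a 95% CI, preferably from an ANCOVA with the baseline value as covariate, and label that model as added after the data were seen. Bowel sounds need it most.
- **RESULTS, baseline:** replace the statement of similarity with the baseline differences and their CIs (step 5 of the working).
- **Data check:** verify the control VAS SDs, 1.71 and 0.94, against source records, and correct or explain them.

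The cost is a few sentences, a few lines of analysis on data already held and one source check. The report loses one supporting argument that it does not need.

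### The conclusion that rinsing accelerates bowel movements goes beyond the data, because the only bowel outcome is a one-minute bowel-sound count taken twice

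*Combined protocol and SAP*

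**What the plan says.** The Official Title lists the outcomes as thirst-related discomfort and "Comfort Level, and Bowel Movement in Individuals Undergoing Abdominal Surgery".

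Data Collection Tools describes four tools. Only the Personal Information Form (item 2) has a bowel component: "The second section included a chart created for recording bowel sounds". Its first section has seven questions, and all seven are named: age, gender, education, diagnosis, preoperative fasting time, postoperative oral intake time and time to start oral intake. None concerns flatus or stool.

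Intervention Procedure gives the method: "each patient's bowel sounds were auscultated for one minute". In the experimental arm this was done before the first of three rinses and again a quarter of an hour after the last. In the control arm it was done at baseline and 75 minutes later.

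Results gives the post-intervention counts and comments on them as "suggesting that oral rinsing enhanced bowel motility, with a large effect size". Its closing paragraph lists "stimulation of bowel motility in the experimental group" among the findings. The Conclusion calls rinsing effective for lessening thirst, "enhancing comfort, and accelerating bowel movements", and then recommends its adoption in routine surgical care.

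**The concern.** The wording grows stronger at each step while the data stay the same. A number of sounds becomes motility, first hedged and then stated as a finding, and finally becomes acceleration of bowel movements. A surgical reader will ordinarily take that last phrase to mean that bowel function returns sooner, yet no time to any bowel event was listed as collected.

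The bowel claim is one of three benefits in the sentence that leads into the routine-care recommendation. It also carries a large standardised effect, which a reader may attach to bowel recovery although it belongs only to the sound count.

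**Working it through.** **1. The reported bowel result.** Inputs from Results, with 49 patients per arm from Study Population and Sample. The reported mean numbers are taken to be one-minute counts, as the method implies.

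| | Experimental | Control |
|---|---|---|
| First measurement, mean (SD) | 3.49 (1.06) | 4.06 (1.52) |
| Second measurement, mean (SD) | 5.98 (1.61) | 3.86 (1.22) |

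Formulas: pooled SD = √((SD₁² + SD₂²)/2); d = difference / pooled SD; t = d × √(49/2).

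- Second measurement: difference = 5.98 − 3.86 = 2.12; pooled SD = √((1.61² + 1.22²)/2) = 1.428; d = 2.12/1.428 = 1.48; t = 1.484 × √24.5 = 7.35. Stated: d = 1.48, t = 7.334. These agree within the rounding of the means and SDs.
- First measurement: difference = 3.49 − 4.06 = −0.57; pooled SD = √((1.06² + 1.52²)/2) = 1.310; d = −0.435; t = −2.15, p = 0.034. Stated: d = 0.44, p < 0.05. These agree.
- Difference in mean change: (5.98 − 3.49) − (3.86 − 4.06) = 2.49 + 0.20 = 2.69 sounds.

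The experimental arm started lower, so the baseline gap does not explain its higher second count.

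**2. Claim against measurement.**

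| Where | Term used | Measured? |
|---|---|---|
| Data Collection Tools; Intervention Procedure | bowel sounds in one minute | yes, at two time points |
| Results | bowel motility | no, inferred from the sounds |
| Conclusion; Official Title | bowel movement(s), with acceleration in the Conclusion | no occurrence or timing of a bowel event listed |

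No section gives a reason for treating the count as a surrogate for either of the lower two rows.

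**3. When the second count was taken.** Take the first rinse as time 0 and ignore the short duration of each rinse. Three rinses 20 minutes apart then fall at 0, 20 and 40 minutes, and 40 + 15 = 55 minutes. Intervention Procedure puts the control re-measurement at 75 minutes and calls this consistent with the experimental arm. The two differ by 75 − 55 = 20 minutes, the length of one further interval. A single phrase therefore cannot describe the time point for both arms, and one tied to the last rinse cannot describe the control arm, which had no rinse.

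**The case against.** The strongest reply is that bowel movement here means intestinal motility. The document never defines it as defecation and uses it alongside motility, with bowel sounds as the only instrument. Likewise, acceleration could describe a rate, since counts in the experimental arm rose from 3.49 to 5.98 per minute. Results also hedges its first mention of motility as a suggestion.

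Both readings are possible, and they limit the criticism. A reader might infer that one of the three headline claims rests on an outcome that was never measured at all. The documents do not support that: on the motility reading, something relevant was measured through a surrogate. But neither reading rescues the Conclusion. Motility was itself only inferred, the surrogate is not justified, a faster rate of sounds is not a faster bowel movement, and the hedge has gone by the closing paragraph of Results and the Conclusion.

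Earlier oral intake in the experimental arm (mean 10.41 against 15.20 hours) might be offered as support. It is not a bowel event, and the document does not link it to the bowel claim.

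It is also fair to say that the document does not state how far the routine-care recommendation depends on the bowel claim. Thirst (d = 3.89) and comfort (d = 3.32) are reported separately.

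**Conclusion.** The point holds as a fault of interpretation and reporting. The trial supports a higher one-minute bowel-sound count at the second measurement: 5.98 against 3.86, a difference of 2.12, or 2.69 in mean change. It does not support a statement about the occurrence or timing of bowel movements, and the size of any such effect cannot be derived from these documents.

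Two stronger inferences should be resisted. The baseline imbalance does not undermine the sound-count result, because it runs against the experimental arm. Nor do the documents show that rinsing leaves bowel recovery unchanged. How closely sounds track recovery is not addressed, so the effect is unknown rather than absent.

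The verdict assumes that the four tools described are all that were used, as the document states, and that no flatus or stool times were recorded elsewhere.

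**What to change.** - **Conclusion:** replace the words on accelerated bowel movements with a higher one-minute bowel-sound count at the second measurement (5.98 v 3.86). State that return of bowel function was not assessed, and do not cite bowel recovery as a basis for the routine-care recommendation.
- **Results:** report the count itself, and present motility only as an inference from it, in the closing paragraph as well.
- **Title:** where it cannot be changed, define bowel movement in the text as the bowel-sound count.
- **Time point:** reconcile the 55 minutes implied by the rinsing schedule with the control arm's 75 minutes, then describe the second measurement separately for each arm.
- **Unreported data:** if times to flatus or stool were in fact recorded, report them.

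The wording changes need no new data and no reanalysis. Reconciling the time point needs a check of what was actually done. The downside is a less favourable conclusion.
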